3.4 STUDY SCHEDULE

A summary of study visits is provided in **Table 2**, and the flowchart of Schedule of Procedures is presented in **Appendix C**.

Table 2: Schedule of study procedures for participants enrolled in the asymptomatic TB transmission in Indonesia and South Africa study

Cross-sectional study of Household Mtb	
Visit 0: Household identification and consent
 
 • Identify geospatial areas for enumeration • Informed consent by household head • Minimal Household enumeration to determine eligibility • Dwelling/House description data
--	--

infection (core study)	
Visit 1: Screening and enrolment
 
 • Consent and enrolment of all adolescents and adults HH members • Demographics • Basic Health Questionnaire • Symptom screening (including W4SS) • Minimal physical examination (weight, height) • Sputum collection for Xpert and MGIT culture • Tongue swab NAAT collection for participants unable or refuse to produce sputum[#] • Digital chest x-ray with computer aided detection (dCXR/CAD) 
Visit 2.1 and 2.2: Community or clinic IGRA measurements (weeks 0-2 and or 8-10)
 
 • Individual assent and parent/ guardian consent for child household contacts • Structured questionnaire on contact patterns with index person and detailed dwelling/House description data • Symptom screening (W4SS modified for children) • If TB symptoms, sputum collection • Weight, height, mid upper arm circumference (MUAC) • Venous blood for IGRA testing (all children at visit 2.1; at week 8-10 (visit 2.2), only repeat IGRA if visit 2.1 IGRA was negative) • Venous blood samples -for HIV^{\$}, cell-free Mtb DNA, Mtb-specific T cells and biobanking • If any symptoms or signs suggestive of TB are identified, refer to the appropriate health facility and provide support for TB investigation and treatment in accordance with national guidelines • Referral for TB preventative therapy (TPT) for all HH contacts of people with TB (visit 2.2) 
Visit 2.3: Community, clinic or telephonic review and referral (weeks 2-14), Provide IGRA status
 
 • Issue any outstanding results for adults • Follow-up on TB treatment or TPT initiation • End of study visit for cross-sectional study
Case-control phenotyping study (sub-study 1) AND Cohort study (sub-study 2)	
Visit 1.1 Facility based clinical assessment (weeks 1-8)
 
 • Individual consent/ assent • Referral to research clinic for phenotyping 
 ◦ Blinded structured questionnaire, include symptoms, quality of life, health outcomes ◦ Physical examination ◦ Collection of 2 sputum samples (Xpert, MGIT culture)* ◦ Collection of samples for novel diagnostic tests 
 ▪ Tongue swabs ▪ Facemask ▪ Exhaled breath condensate ▪ Venous blood – HIV; VL; HbA1C; FBC/smear; Mtb cell free DNA; Mtb-specific T cell activation, biobanking specimens ◦ Physician review of participant's TB screening results • Clinical referral for TB and non-TB care • Telephonic review of linkage to care and well-being • Electronic / physical record review to confirm TB treatment initiation and completion
TB-U Cohort study (sub-study 2)	
Visit 1.2, to 1.5: Longitudinal follow-up (Months 3, 6, 9 & 12)
 
 • Clinical assessment including symptoms, quality of life, health outcomes • Physical examination • Sputum samples x 2 (Xpert, MGIT culture) • Venous blood – Mtb cell free DNA; Mtb-specific T cell activation, biobanking specimens • Digital chest x-ray • Facemask and Exhaled Breath Condensate, in a subset of participants • Physician review • Clinical referral for TB or non-TB care

Tongue swabs will only be collected if approved by WHO and/or national authorities (South Africa or Indonesia) and in participants unable or refuse to produce sputum

* If eligibility is based on a positive tongue swab collected due to unsuccessful sputum collection at visit 1.0, three sputum samples will be collected at visit 1.1

[figure not shown]
\$ HIV testing in children will only be performed in South Africa

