Cross-sectional study of Household Mtb infection (core study)	
Community screening: Adolescents and adults (≥ 15 years) who reside in households located within the study areas in each setting
 
Child contacts: Children (2-14 years) who are household contacts of people with sTB-C, people with aTB-C or of randomly selected adults in households without TB
	
1. Adolescent/Adult participants for community screening
 
Inclusion criteria:
 
 1. Age ≥ 15 years 2. Residence in the designated study area 3. Residence in a household with children (2-14 years) 
Exclusion criteria:
 
 1. Unable or unwilling to consent (>18 years) 2. Unable to unwilling to assent (15-17 years) 3. Parent or guardian unwilling to consent (15-17 years) 4. Residence in a household with a participant in a TB vaccine trial (currently or previous 2 years) 
2. Child household contacts
 
Inclusion criteria:
 
 1. Age 2-14 years 2. Household residence with an adolescent/adult participant with: 
 a. aTB-C, or b. sTB-C, or c. an adolescent/adult participant who has been selected as a healthy control (no TB) 
Exclusion criteria:
 
 1. Unable or unwilling to assent (≥ 7 years) 2. Parent/guardian unable or unwilling to consent 3. Residence in household in which any resident has been diagnosed with TB within the past 2 years 4. Residence in a household with more than one adolescent/adult with current co-prevalent TB-C
Case-control phenotyping study (sub-study 1)	Adolescents and adults (≥ 15 years) who participated in cross-sectional study of household Mtb infection (core study)	
1. Participants with aTB-C
 
Inclusion criteria:
 
 1. Adolescent/adult participant in TB screening 2. Screening W4SS negative 3. Screening sputum Xpert positive (any grade) OR Mtb MGIT positive* OR tongue swab NAAT positive 
2. Participants with sTB-C
 
Inclusion criteria:
 
 1. Adolescent/adult participant in TB screening 2. Screening W4SS positive 3. Screening sputum Xpert positive (any grade) OR Mtb MGIT positive* OR tongue swab NAAT positive

Study	Study Population	Eligibility Criteria

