Most participants will be categorized according to their screening results which include Xpert or tongue swab NAAT and dCXR/CAD. These results are expected to be available within approximately two weeks of sample collection. The **MGIT culture results** may require up to 6 weeks to become available.-Those participants that are newly diagnosed with TB (as aTB-C, sTB-C) based on the MGIT culture results will be considered for the sub-study 1 and 2; while their child household contacts will be invited to undergo IGRA assessments. If the adolescent or adult MGIT result is positive within 2 weeks of collection, the child HHC will be invited to participate in visits 2.1 and 2.2. If the MGIT result becomes positive later than 2 weeks, only visit 2.2 will be conducted, due to study visit scheduling constraints.

All adolescent/adult participants with positive screening results (Xpert; tongue swab, MGIT) will be referred to Visit 1.1 within 2 weeks of their positive result and will receive appropriate referrals at the end of the study visit. Participants who are not eligible for any additional study visits will have their screening results returned, appropriate referrals will be made as needed, and participants will be thanked for their participation. When all results are normal and no referrals are required, participants may be informed of their results by telephone or SMS.

Households of **aTB-C participants (aTB-C household)** and **sTB-C participants (sTB-C household)**, as well as selected **noTB participants (Control Household)** serving as controls, will undergo a follow-up visit (Visit 2.1).

At the **community or clinic visit (visit 2.1; Figure 3)**, if the child or children meet the eligibility criteria, initially parental/individual assent and/or guardian consent will be obtained for each child during this visit.

Figure 3. Core study participant flow, including IGRA testing among child contacts.

★ If the adolescent/adult MGIT is positive within 2 weeks, the child household contact will be eligible for both visit 2.1 and 2.2

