A **structured questionnaire** will be administered to an adult household member to collect information on household characteristics, living arrangements, and factors influencing Mtb transmission. Data will include dwelling type, ventilation, contact patterns, hygiene practices, and key individual factors such as socioeconomic status, health history, vaccination, and exposure risks. Social mixing patterns and time spent at home versus in the community will also be captured through the interviewer-administered questionnaire.

TB symptom screening will be conducted using a version of the W4SS adapted for children.

Symptomatic children will have **sputum collection** attempted for testing with Xpert and MGIT. All children will have the height (or length if appropriate), weight and mid-upper arm circumference (MUAC) measured, where applicable.

Between 4 to 10 mL of **venous blood** (no more than 1ml/kg) will be collected from all children for interferon-gamma release assay (IGRA) testing, analysis of cell-free Mtb DNA and Mtb-specific T cells, and for biobanking.

In **South Africa**, **HIV testing** will be performed for children where parental or guardian consent and child assent have been obtained. Testing will be conducted with age- and maturity-appropriate pre- and post-test counselling in accordance with national guidelines

Children with a **negative baseline IGRA** result will be revisited 8–10 weeks later (**Visit 2.2**) for repeat TB symptom screening and collection of a second blood sample for IGRA, cell-free Mtb DNA, Mtb-specific T cells, and biobanking. If the child is symptomatic at that visit, sputum collection for Xpert and MGIT will again be attempted. At both study visits, children identified with TB symptoms will be referred to the appropriate health facility for further TB assessment. The study team will provide support to strengthen local healthcare facilities by building capacity in the investigation and management of children with TB symptoms in line with national guidelines.

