3.8 STUDY OUTCOMES/ ANALYSES

The study is designed to assess both the transmission of Mtb within households and the diagnostic performance of current and novel tools for detecting asymptomatic TB. The outcomes are grouped into primary and additional outcomes categories as outlined below.

CORE STUDY

Primary endpoint: Cumulative prevalence of child household contact IGRA positivity or confirmed TB (TB-C) at 10 weeks after diagnosis of the index case.

Additional outcomes/ analyses:

- (1) Proportion of children that convert from negative IGRA status at baseline to a positive IGRA status at 10-week visit.
- (2) Proportion of children with a positive plasma cell free Mtb DNA assay and positive Mtb-specific T cell activation assay, stratified by household group.
- (3) Whole genome sequencing of Mtb isolates from people with TB-C and household contacts.

CASE-CONTROL PHENOTYPING STUDY (SUB-STUDY 1)

- (4) Sensitivity, specificity, positive predictive value, negative predictive value, yield, feasibility, acceptability of digital chest x-ray with computer aided diagnosis (dCXR/CAD), sputum Nucleic Acid Amplification Test (NAAT), Mycobacteria Growth Indicator Tube (MGIT), tongue swab NAAT, and bioaerosol collection facemask mask NAAT to detect aTB-C.
- (5) Symptoms, health outcomes quality of life, comorbidities, nutritional status, and TB history, relative to group and W4SS status at screening.

(6) Proportion and characteristics of participants with detectable exhaled breath condensate lipoarabinomannan (LAM), positive plasma cell free Mtb DNA assay, positive Mtb-specific T cell activation assay and additional blood-based TB biomarkers, stratified by group.

TB UNCONFIRMED (TB-U) COHORT (SUB-STUDY 2)

(7) Time to event and factors associated with microbiological or clinical progression in participants with initially untreated aTB-U.

(8) Plasma biomarkers (including cell free Mtb DNA, Mtb-specific T cells, transcriptional signatures) that correlate with progression from aTB-U in the 12 months after TB screening

(9) Proportion and characteristics of participants with TB screening results suggestive of (TB-U) who have a subsequent positive sputum GeneXpert Ultra, sputum MGIT, tongue swab NAAT or Bioaerosol collection facemask mask NAAT.

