APPENDIX C : SCHEDULE OF STUDY PROCEDURES

Table 7: Schedule of Study Procedures

Study	Cross- Sectional study (core study)					Phenotypic (Sub-study 1)	Cohort (Sub-study 2)			
	Adolescents & Adults (> 15 yrs.)		Children (2-14 years)				Adolescents & Adults			
Visit	Visit 0	Visit 1	Visit 2.1	Visit 2.2	Visit 2.3	Visit 1.1	Visit 1.2	Visit 1.3	Visit 1.4	Visit 1.5
Time point		screening	Week 0-2*	Week 8-10	Week 2-14	Week 1-8	Month 3	Month 6	Month 9	Month 12
Household census and consent	x									
Informed consent / assent		x	x	x ^b		x				
Demographics		x								
Medical History		x				x				
Structured questionnaire			x	x ^b		x				
TB Symptom Screening (W4SS)		x	x	x						
TB Symptom Assessment (full)						x	x	x	x	x
Clinical Assessment incl. quality of life, functional status							x	x	x	x
Physical Examination -limited		x	x	x ^b						
Physical Examination - full						x	x	x	x	x
Sputum sampling – NAAT & MGIT		x	x ^a	x ^a		x	x	x	x	x
Blood sample- HIV Counselling and testing\$			x	x ^b		x				
Blood sample- IGRA			x	x ^c						
Blood sample – HbA1c, full blood count						x				
Blood sample – Mtb-specific T cell activation; Mtb cell free DNA; biobanking			x	x		x	x	x	x	x
Digital X-Ray with CAD		x					x	x	x	x
Novel tests – tongue swab NAAT; facemask; exhaled breath condensate						x	x ^d	x ^d	x ^d	x ^d
Physician review						x	x	x	x	x
Referral to DOH – TB assessment, as required			x	x	x	x	x	x	x	x
Referral to DOH – TPT, as required			x	x	x					

x^a: if child is symptomatic; **x^b:** if adult diagnosed on MGIT> 2 weeks after collection, child consent/assent, structured questionnaire and HIV will be taken at visit 2.2; **x^c=** : IGRA repeated at visit 2.2 if negative at visit 2.1 **x^d:** facemask and exhaled breath condensate to be collected at all study visits in a subset of TB-U cohort participants (first n=100); * If adolescent/ adult MGIT positive within 2 weeks the child HHC will be eligible for visit 2.1 & 2.2; if MGIT positive> 2weeks, the child HHC will only attend visit 2.2; \$: HIV testing of children will only occur in South Africa

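### The second IGRA is tied to a negative first result, so a child whose first IGRA is indeterminate, failed or not obtained is left without a valid IGRA for the primary endpoint

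*Protocol*

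**What the plan says.** Three places set the rule for the second IGRA.

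- Section 3.4, Table 2: "at week 8-10 (visit 2.2), only repeat IGRA if visit 2.1 IGRA was negative".
- Section 3.5: children with a negative baseline "result will be revisited 8–10 weeks later". Here the revisit itself, and not only the blood test, is described for baseline-negative children.
- Appendix C, Table 7, footnote c: "IGRA repeated at visit 2.2 if negative at visit 2.1".

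Section 3.8 defines the primary endpoint as "Cumulative prevalence of child household contact IGRA positivity or confirmed TB (TB-C) at 10 weeks after diagnosis of the index case". The confirmed-TB route depends on sputum, and under section 3.5 it is symptomatic children who "will have sputum collection attempted for testing with Xpert and MGIT".

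Households whose index case is found late by culture follow a different schedule: "If the MGIT result becomes positive later than 2 weeks, only visit 2.2 will be conducted". Their children have one IGRA only, at Visit 2.2.

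No visible text mentions an indeterminate, invalid or failed IGRA, or a redraw. The protocol does foresee the parallel problem for culture: a footnote to the case definitions says what happens when one of the three MGIT cultures is contaminated.

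**The concern.** The rule works for two possible results. A positive first IGRA settles the endpoint, and a negative one leads to the second test. A first test that gives no usable answer fits neither branch. Read literally, the rule withholds the second test from the children who most need it, because they have no result at all.

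The primary outcome is at stake. This is a rule about data collection. A statistical analysis plan can say how missing results are handled, but it cannot supply a blood test that was never taken. It also leaves open whether such a child is dropped or counted as not positive, and the two choices give different estimates.

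**Working it through.** **Does the rule reach these children?** Take an asymptomatic child whose Visit 2.1 IGRA is indeterminate. Table 2 and Table 7 footnote c allow a second IGRA only after a negative result, so none is done. Without symptoms no sputum is attempted, so confirmed TB cannot be established by the study either. The child reaches week 10 with neither component of the endpoint determined.

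**Would a Visit 2.2 test be enough?** By the protocol's own logic, yes. In late-culture households a single IGRA at Visit 2.2 is the only one taken. Table 7 also marks blood for the T-cell and cell-free DNA assays at Visit 2.2 without a condition on the first IGRA.

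**How many children?** Planned numbers (Protocol Summary): 600 households × 1.5 = 900 children in Bandung and 600 × 2.5 = 1,500 in KwaZulu-Natal. Both reproduce exactly. The protocol gives no invalid rate, so the rates below are assumptions.

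| Assumed share of first IGRAs | Bandung | KwaZulu-Natal | Total |
|---|---|---|---|
| 2% | 18 | 30 | 48 |
| 5% | 45 | 75 | 120 |
| 10% | 90 | 150 | 240 |

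These are slight upper figures: children tested only at Visit 2.2 are in the denominators, and their number is not stated.

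**Power, if affected children are missing at random.** Inputs (section 5.1, Tables 3 and 4): 150 aTB and 300 control households; children per household 1.5 (SD 0.7) and 2.5 (SD 1.6); ICC 0.30; IGRA positivity 20% v 32% in Bandung and 7% v 14% in KwaZulu-Natal. Two-sided alpha of 0.05 is assumed. With m the mean number of children per household and CV = SD/m, the design effect is 1 + ((CV² + 1)m − 1) × ICC.

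- Bandung: CV² = (0.7/1.5)² = 0.218; design effect 1 + (1.218 × 1.5 − 1) × 0.30 = 1.248; effective n in the aTB group 150 × 1.5/1.248 = 180.3; power 0.859. Table 4 prints 80%; the difference detectable with 80% power is 11.05%, so the printed 12% fits rounding up.
- KwaZulu-Natal: CV² = 0.410; design effect 1.757; effective n 375/1.757 = 213.4; power 0.797, which reproduces the stated 80%.

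Now remove 10% of children.

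- With CV held fixed, m becomes 1.35 and 2.25. Power falls from 0.859 to 0.838 in Bandung and from 0.797 to 0.780 in KwaZulu-Natal, a loss of about 2 points or less.
- If children are lost independently of one another, CV rises slightly. The design effect is then 1 + 0.9 × (original design effect − 1), which is 1.223 and 1.681. Effective n is 202.5/1.223 = 165.5 and 337.5/1.681 = 200.7, and power is 0.829 and 0.773, a loss of 3.0 and about 2.3 points.

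**If affected children were instead counted as not positive**, with equal rates in all groups, each prevalence would be multiplied by (1 − rate). Table 4's Bandung difference of 12 points would become 12 × 0.98 = 11.8 at 2% and 12 × 0.90 = 10.8 at 10%. The aTB/sTB risk ratio would not change, because the factor cancels. The protocol does not say it will count them this way.

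**The case against.** The strongest reply is that this is a wording gap that practice will close. Section 3.6 refers assay conduct to SOPs and manufacturer instructions, which may deal with failed tubes. Figure 3, on IGRA testing of child contacts, is not visible in the text at hand and could show a branch for invalid results. Completing a test that never gave a result is arguably not repeating it. Some of this stands: a redraw outside the visible text cannot be excluded. But the three visible statements agree with one another, Table 2 uses the word *only*, and a site following them would not do the second IGRA.

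Four stronger readings are tempting, and the documents do not support them.

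- **The loss falls mainly on the youngest children or those with HIV.** The nearest text is the blood-volume limit of 1 mL/kg and child HIV testing in South Africa only. Neither says who is more likely to have an invalid result.
- **These children can have no endpoint at all.** Confirmed TB still counts, although the route is narrow.
- **These children are never seen again.** Only section 3.5 limits the revisit. Table 2 places referral for preventive therapy of all household contacts of people with TB at Visit 2.2, and Table 7 schedules symptom screening and other blood there without that condition.
- **The comparison between groups is biased.** The retest rule is the same in every household group, and no difference in invalid rates is shown.

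**Conclusion.** The point holds as a defect in a stated data-collection rule. Followed literally, the protocol gives no second IGRA to a child whose first gave no valid result. That child has no valid IGRA for the primary endpoint unless TB is confirmed. How many children this affects depends wholly on the assumed 2% to 10%. The power cost is modest if the loss is random, so power is not the reason to act. The reason is that these are missing primary outcomes that a test at an existing visit could largely avoid. Confidence is high on the wording of the rule and low on its numerical effect.

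**What to change.** In Table 2 (section 3.4), section 3.5 and Table 7 footnote c, replace the condition *if negative* with *if not positive*. Every child without a valid positive Visit 2.1 IGRA (negative, indeterminate, failed or not obtained) is then seen and tested at Visit 2.2.

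Add two counting rules:

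- A child with no valid IGRA at either visit and no confirmed TB is missing in the primary analysis, not negative.
- A child without a valid negative baseline IGRA is left out of the negative-to-positive conversion outcome in section 3.8. A positive Visit 2.2 result in such a child counts towards the primary endpoint but is not a conversion.

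The cost is three wording changes, two sentences and, under the assumed rates, about 48 to 240 more IGRAs at a visit that already exists. The change does not help children in late-culture households: they have only Visit 2.2, so an invalid result there has no later scheduled test. Covering them would need a separate redraw provision.

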3.5 STUDY PROCEDURES

Large scale community screening will be conducted among adolescents and adults aged 15 years and older who reside in the study areas and in households (HH) with children aged 2–14 years. To better understand Mtb transmission, households will be enrolled from contiguous geographic areas, allowing for the assessment of transmission while minimising geographic variability and potential confounding introduced by non-adjacent areas.

Prior to entering each selected area, the study team will obtain permission from the local area leader or community authority. Study areas will be mapped using Quantum Geographic Information System (QGIS) software or other equivalent geographic information system tools to define boundaries and identify households for enumeration. All households within these contiguous areas will be visited to enumerate inhabitants (**Figure 2**). Household enumeration will be part of visit 0 and may be done on the same date as visit 1.0. Informed consent will be obtained from the household head before any study activities are conducted. Following consent, household enumeration will be performed to determine eligibility for participation, and minimal dwelling characteristics will be recorded. The GPS coordinates of participating households will also be documented as part of the household-level assessment.

Figure 2. Schematic overview of participant flow across study components

At the **screening and enrolment (visit 1.0)**, all adolescent and adult household members will be approached for informed consent/ assent. Following enrolment, demographic information and responses to a basic health questionnaire will be collected. Participants will undergo symptom

screening using W4SS. They will also answer a question about the presence and nature of any additional symptoms they are experiencing, and whether any of their symptoms have prompted them to seek health care. A minimal physical examination, including measurement of weight and height, will be performed. Following coaching, each participant will provide a minimum of 3ml sputum/respiratory tract sample for Xpert and MGIT culture testing

If following coaching, the participant is still unable or refuses to produce a 3ml sputum sample, a tongue swab will be collected for NAAT. Tongue swabs will only be collected if their programmatic use has been approved by WHO and/or national authorities (South Africa or Indonesia), and in participants unable or refuse to produce sputum.

In addition, a digital chest X-ray with computer-aided detection (dCXR/CAD) will be conducted as part of the TB screening assessment. All dCXR/CAD X-Rays which are reported as suggestive of TB by the CAD software will be reviewed by a radiologist.

Within 2 weeks of the screening visit (visit 1.0), the **adolescent/adults** screened will be categorised into one of 5 screening groups ([Figure 2](#)).

- (1) **aTB-C Participant:** W4SS screening - negative; Xpert -positive (any grade) OR tongue swab-NAAT – positive; dCXR/CAD – any result
- (2) **sTB-C Participant:** W4SS screening - positive; Xpert -positive (any grade) OR tongue swab-NAAT – positive ; dCXR/CAD - any result
- (3) **aTB-U Participant:** W4SS screening - negative; Xpert -negative-OR tongue-swab NAAT – negative; dCXR/CAD – suggestive of TB
- (4) **sTB-U Participant:** W4SS screening -positive; Xpert-negative OR tongue-swab NAAT – negative; dCXR/CAD – suggestive of TB
- (5) **noTB Participant:** W4SS screening -negative; Xpert – negative OR tongue swab NAAT – negative ; dXR/CAD – normal

Adult and adolescent participants (≥15 years) will be identified ([Figure 2](#)) for potential enrolment into either the case-control phenotyping-study (Sub-study 1; aTB-C, sTB-C) or the TB-U cohort study (Sub-study 2; TB-U). For each aTB-C participant, a control participant (1:2 ratio) will be randomly selected among noTB participants within the neighbourhood (250–700 m radius depending on the population density, using GIS coordinates) of the aTB-C participant's household.

The **child household contacts (aged 2–14 years)** of those with aTB-C and their controls, and sTB-C will be eligible for inclusion in the cross-sectional study (IGRA assessments) of household Mtb infection (core study).

[figure not shown]
Most participants will be categorized according to their screening results which include Xpert or tongue swab NAAT and dCXR/CAD. These results are expected to be available within approximately two weeks of sample collection. The **MGIT culture results** may require up to 6 weeks to become available.-Those participants that are newly diagnosed with TB (as aTB-C, sTB-C) based on the MGIT culture results will be considered for the sub-study 1 and 2; while their child household contacts will be invited to undergo IGRA assessments. If the adolescent or adult MGIT result is positive within 2 weeks of collection, the child HHC will be invited to participate in visits 2.1 and 2.2. If the MGIT result becomes positive later than 2 weeks, only visit 2.2 will be conducted, due to study visit scheduling constraints.

All adolescent/adult participants with positive screening results (Xpert; tongue swab, MGIT) will be referred to Visit 1.1 within 2 weeks of their positive result and will receive appropriate referrals at the end of the study visit. Participants who are not eligible for any additional study visits will have their screening results returned, appropriate referrals will be made as needed, and participants will be thanked for their participation. When all results are normal and no referrals are required, participants may be informed of their results by telephone or SMS.

Households of **aTB-C participants (aTB-C household)** and **sTB-C participants (sTB-C household)**, as well as selected **noTB participants (Control Household)** serving as controls, will undergo a follow-up visit (Visit 2.1).

At the **community or clinic visit (visit 2.1; Figure 3)**, if the child or children meet the eligibility criteria, initially parental/individual assent and/or guardian consent will be obtained for each child during this visit.

Figure 3. Core study participant flow, including IGRA testing among child contacts.

★ If the adolescent/adult MGIT is positive within 2 weeks, the child household contact will be eligible for both visit 2.1 and 2.2

A **structured questionnaire** will be administered to an adult household member to collect information on household characteristics, living arrangements, and factors influencing Mtb transmission. Data will include dwelling type, ventilation, contact patterns, hygiene practices, and key individual factors such as socioeconomic status, health history, vaccination, and exposure risks. Social mixing patterns and time spent at home versus in the community will also be captured through the interviewer-administered questionnaire.

TB symptom screening will be conducted using a version of the W4SS adapted for children.

Symptomatic children will have **sputum collection** attempted for testing with Xpert and MGIT. All children will have the height (or length if appropriate), weight and mid-upper arm circumference (MUAC) measured, where applicable.

Between 4 to 10 mL of **venous blood** (no more than 1ml/kg) will be collected from all children for interferon-gamma release assay (IGRA) testing, analysis of cell-free Mtb DNA and Mtb-specific T cells, and for biobanking.

In **South Africa**, **HIV testing** will be performed for children where parental or guardian consent and child assent have been obtained. Testing will be conducted with age- and maturity-appropriate pre- and post-test counselling in accordance with national guidelines

Children with a **negative baseline IGRA** result will be revisited 8–10 weeks later (**Visit 2.2**) for repeat TB symptom screening and collection of a second blood sample for IGRA, cell-free Mtb DNA, Mtb-specific T cells, and biobanking. If the child is symptomatic at that visit, sputum collection for Xpert and MGIT will again be attempted. At both study visits, children identified with TB symptoms will be referred to the appropriate health facility for further TB assessment. The study team will provide support to strengthen local healthcare facilities by building capacity in the investigation and management of children with TB symptoms in line with national guidelines.

A community, or clinic-based follow-up visit or telephonic contact will be conducted between weeks 2 and 14 (**Visit 2.3**) for participants with positive results. This visit will be used to provide IGRA and sputum results (where sputum was collected) and to confirm that appropriate referral to the local health clinic for TPT initiation or TB treatment, as indicated, has occurred. The study team will provide support to strengthen local health care facilities by building capacity in the provision of TPT for household contacts of participants diagnosed with TB, in accordance with national guidelines.

In South Africa, HIV results will be provided with post-test counselling using language appropriate to the child's age and maturity. Children aged 12–14 years may receive their results without a parent or guardian present but will be encouraged to involve their parent or guardian in the discussion and ongoing support.

Participants with negative results will be contacted via telephone or SMS. This visit will mark the End-of-Study visit for household contacts.

SUB-STUDIES 1 and 2

Within two weeks of TB screening, eligible participants will be invited to attend the research clinic for **Visit 1.1**. Participants will remain blinded to their screening results at the time of the visit. At Visit 1.1,

individual consent or assent will be obtained for participation in the sub-studies. This visit will include all participants being enrolled in either Sub-study 1 (aTB-C, sTB-C, and control participants) or Sub-study 2 (TB-U participants).

At the clinic, a **blinded structured questionnaire** will be administered to collect detailed information on symptoms, quality of life, functional status, and health outcomes. This will be followed by a comprehensive physical examination, including assessment of vital signs, height, weight, lymphadenopathy, and breath sounds. Two samples, either an early-morning and spot specimen or two spot specimens, as per site procedures will be collected for Xpert and MGIT culture testing. Participants whose screening molecular test was a positive tongue swab NAAT, will have 3 sputum specimens collected.

Additional samples will be obtained for novel diagnostic assays, including tongue swabs, bioaerosol collection using a facemask, and exhaled breath condensate. Exhaled breath condensate (EBC)samples will be collected by trained study staff using a hand-held or desktop EBC device. Participants will breathe tidally, with or without coughing, into a straw connected to the device for 10 minutes, repeated twice. Venous blood (40mL) will be collected for HIV, viral load testing, HbA1c, full blood count, Mtb cell-free DNA, Mtb-specific T cell activation and biobanking.

A study physician will review each participant's TB screening results and advise the participant of their results at the end of the visit. They will ensure appropriate clinical referral for TB and non-TB care in line with national guidelines. The study physician will conduct scheduled remote reviews of all sputum results and the clinically reportable blood results (HbA1c, HIV, viral load, full blood count). If a positive result is identified at any time, the physician will contact the participant to ensure prompt referral to a health facility, accompanied by all relevant test results.

Ongoing contact will be maintained with all TB-C participants to encourage initiation of TB treatment and continue to assess participant well-being until linkage to care and commencement of TB treatment is documented (verification by chart review or electronic record linkage). TB treatment outcomes will be ascertained in all those that start TB treatment. Participants who decline TB treatment despite referral will be offered continued follow-up and monitoring within the TB-U cohort study. When all results are normal and no referrals are required, participants may be informed of their results by telephone or SMS.

Once all MGIT results from Visit 1.1 have final results, the study team will confirm study case definitions and communicate with participants regarding their next steps in the study. Participants in Sub-study 1 will complete their clinic-based visits after Visit 1.1 (other follow-ups telephonic or as the research team conducts IGRA assessments in the community). Participants enrolled in Sub-study 2 will continue follow-up in accordance with the established schedule, attending Visits 1.2 through 1.5 as outlined in schedule of events ([Table 3; Appendix C](#)).

TB-UNCONFIRMED (TB-U) COHORT STUDY (SUB-STUDY 2)

Eligible participants for this TB-U cohort study will be evaluated in the research clinic every three months (month 3,6,9 &12) for one year (**Visits 1.2-1.5**) to monitor progression.

At each follow-up visit, participants will undergo a structured clinical assessment, including an interim health history, review of recent antibiotic or TB treatment use, detailed symptom screening, evaluation of quality of life, functional status, and health-seeking behaviour.

A comprehensive physical examination will be performed, including assessment of vital signs, height, weight, lymphadenopathy, and breath sounds.

Sputum specimens will be collected for TB phenotyping, consisting of two samples, either an early-morning and spot specimen or two spot specimens, as per site procedures. Venous blood will be drawn for phenotyping assays, including Mtb-specific T cell activation, Mtb cell-free DNA, and samples for biobanking. A dCXR/CAD will be performed at each visit. Facemask and Exhaled breath condensate will be collected from a subset of participants

A study physician will regularly review each participant's clinical, radiological, and microbiological results, including sputum findings, to assess disease progression or resolution. If a positive sputum result is identified at any time, the participant will be promptly contacted and referred for TB evaluation and treatment initiation in line with national guidelines. Referrals will be made for non-TB care as required. Ongoing contact will be maintained with all participants referred for TB treatment to encourage initiation of TB treatment and to continue to assess participant well-being until linkage to care and commencement of TB treatment is documented (verification by chart review or electronic record linkage). Individuals who commence TB treatment during follow-up will be considered to have reached the progression endpoint and will not continue with further TB-U cohort study visits.

Visit 1.5 will serve as the End-of-Study visit for participants in Sub-study 2. At this visit, clinically relevant results will be returned, participants will be counselled to seek clinical care if any symptoms or physical conditions worsen, and they will be thanked for their participation

